**Randomization**: At each site, enrolled drivers (with their family members) will be randomly assigned in equal numbers to the DDA or control arm (Figure 4). To reduce bias and aim for balance among arms, we will randomize patients in blocks with randomly varied block sizes of 4 and 6. While RAs delivering the intervention to patients cannot be blinded to treatment, we will conceal allocation using a centralized, computer-generated list that RAs will access only after enrollment. Other study staff, including a different RA (whenever possible) doing follow-up calls, will be blinded to study arm.

**Baseline Measurements & Intervention**: The driver and family member will be randomized to the same arm but will complete all study measures and interventions separately from each other. For each participant (including those enrolled in person as well as those enrolled remotely by phone), the RA will use a study tablet or laptop to administer the introductory questionnaire (Figure 4, Table 3). In the intervention arm, participants will then complete the web-based DDA; control group participants will be directed to the NIA "Older Drivers" website. After completing the DDA or website review, all participants in both arms will answer questions about their knowledge, values, and plans related to driving cessation (Table 3). For family members, questions will generally be about the older driver, though there will be specific questions concerning their relationship, frequency of contact, and possible co-dependence for transportation. Whenever possible, participants will receive a printed handout of either their DDA results or the NIA webpage (for those enrolled in person) or will receive instruction from the RA about how to save an electronic copy of the DDA results or the NIA webpage (for those enrolled in person) or the NIA webpage (for those enrolled remotely by phone).

**Identifying driving risk**: At the request of the DSMB, the study team will use American Academy of Neurology (AAN) guidelines to identify drivers who are at moderate risk for being unsafe to drive (https://www.aan.com/PressRoom/home/GetDigitalAsset/8471). Per AAN

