AUTO Study Protocol: Version Date: 12/22/21 PI: [name], MPH COMIRB No: 19-0059 guidelines, "moderate risk" will be a Clinical Dementia Rating (CDR) of 0.5 with "few" to "several" risk factors, or a CDR of 1.0 with "no" or "few" risk factors". AUTO uses the 5-minute MoCA, rather than the CDR or MMSE. MoCA scores of 18-25 suggest "mild" impairment while 10-17 suggest "moderate". Drivers must score ≥21 on the 5-minute MoCA to be eligible, therefore, participants with "moderate" cognitive impairment (as defined by AAN guidelines) are not enrolled.

As recommended by DSMB, we will identify participants with a MoCA score of 21-25 as having possible mild cognitive impairment. For those participants, we will review any additional AAN driving risk factors (see table below).

Drivers with MoCA scores of 21-25 and ≥3 risk factors will be identified as "moderate risk" for the purposes of these safety checks. For participants identified as having moderate risk, we will perform an ad hoc review. We will report these findings to the DSMB at the regularly scheduled intervals unless there is an AE/SAE as previously described.

For participants meeting these thresholds, we will recommend a driving evaluation and provide the participant with information from ADED (Association for Driver Rehabilitation Specialists) about local resources. We will request participants share the subsequent driving evaluation results, although participants may remain in the study if

they decline either the evaluation or data sharing. Any participant who receives a recommendation for a driving evaluation will be noted in the study database so we can later perform sensitivity analyses to see if that recommendation (or the evaluation, if obtained) affects the observed efficacy of the study intervention (driving decision aid).

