physical limitations (including site, reflexes and strength), or who mentions problems with driving. In such cases, the research staff member would document the date and specific observations and review the issue with the Site PI. If the concerns are deemed relatively mild, the study team will provide the participant with information on community resources for driving assessment and rehabilitation and will recommend that they discuss their driving with their primary care provider. If the concerns are deemed more serious than "relatively mild," the study team would similarly provide information (including specific concerns) to the participant with the written recommendations that they talk with their primary care provider and/or have a driving safety evaluation and that they not drive until cleared. The informed consent form gives participants the option of allowing the research team to contact a primary care provider and/or another designee if the investigators' concerns about driving risks are more serious than "relatively mild." If consent was given, the study team would reach out to the designated person or people to express their concerns about the subjects' driving safety. Otherwise, additional survey responses will not be shared with anyone who is not involved with the study (including physicians, family members, or hospital or law enforcement authorities) unless specifically requested by the participant, this includes the co-enrolled family member or friend.

This study will enroll older adults who potentially may experience mild to moderate levels of cognitive impairment, creating a potential risk for informed consent for study participation. Level of impairment will be measured through administration of the 5-minute MoCA during an initial phone screen; the participant must score ≥21 to be eligible to be scheduled for an enrollment visit. While completing the consent process during the initial study interview (in person or remotely, via phone), staff will ask a series of questions to determine understanding of study procedures. In the event there is cognitive concern, the participant will not be allowed to enroll in the study.

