At each follow up for all drivers and study partners, a 5-minute MoCA will be repeated to determine current cognitive impairment. As all participants have completed informed consent at initial enrollment, potential diminished cognitive capacity does not limit the participant's right to continued participation in follow up calls. During consent at enrollment, participants will have reviewed study requirements, tasks, duration, and an explanation that all participants have the right to continue or withdraw as they wish. Therefore, cognitive impairment will not automatically withdraw a participant from the study. Further, this study poses minimal risk to the participant. In the event that severe cognitive impairment disrupts the research team's ability to collect follow up data from the participant, the study team may choose to discontinue all or specific portions of follow-up procedures.

Because of the study's affiliation with clinical sites, there is the potential risk of coercion. We will minimize this risk by being very clear that participation is completely voluntary, separate from their clinical care, and that a participant can withdraw from the study at any time. Additionally, we will make clear that the patient's clinical care will not be impacted by the decision to participate or not to participate. No clinicians or providers from the participating clinics will be involved in the consenting of patients. There will be no exchange of payment for study participant referrals.

This study will not involve pregnant women, human fetuses, neonates, children, or prisoners. Study participation will not interfere with clinical care. The study informed consent form will include a written description of all of these risks, including the potential for eventual driving AUTO Study Protocol: Version Date: 12/22/21 PI: [name], MPH COMIRB No: 19-0059 cessation due to study participation, and all of these risks will be discussed during the informed consent process. This study will not enroll older adults with severe cognitive impairment.

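### The sensitivity analysis by driving evaluation obtained would condition on a choice made after randomisation; base it on a pre-randomisation flag and report uptake by arm

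*Combined protocol and SAP*

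**What the plan says.** Under Identifying driving risk (Study Design and Research Method), a rule added at the request of the DSMB selects drivers for a recommended driving evaluation: "Drivers with MoCA scores of 21-25 and ≥3 risk factors will be identified" as moderate risk. Drivers may stay in the study if "they decline either the evaluation or data sharing". Everyone who receives a recommendation is marked in the database, so that the team can run "sensitivity analyses to see if that recommendation (or the evaluation, if obtained) affects the observed efficacy of the study intervention". No model, outcome, time point or analysis set is given.

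Other places that bear on timing:

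- **First MoCA.** Risks to Human Subjects: "Level of impairment will be measured through administration of the 5-minute MoCA during an initial phone screen". This precedes randomisation, which follows enrolment (Enrollment, and Consent).
- **Later MoCA.** The same section: "At each follow up for all drivers and study partners, a 5-minute MoCA will be repeated to determine current cognitive impairment". It does not say whether a later score can prompt a recommendation.
- **Second route.** The same section lets staff concern lead to advice that the driver talk with a primary care provider and/or "have a driving safety evaluation and that they not drive until cleared". No time limit is set.
- **Blinding.** Randomization: "While RAs delivering the intervention to patients cannot be blinded to treatment".
- **Main analysis.** Analysis for Aim 1 is by intention to treat. The primary outcome (Aim 1a) is DCS below 25 immediately after the intervention.

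**The concern.** The sensitivity analysis has two branches. The first groups drivers by whether an evaluation was recommended. If that status is fixed before randomisation, it is an ordinary baseline subgroup and the arm contrast within it stays randomised.

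The second branch groups drivers by whether they had the evaluation. That is decided after randomisation, by the driver. Table 1 shows that the DDA deals with warning signs and asks drivers to rate their concern about crashes, and Aim 1c expects it to lead to changes in driving. It could therefore alter who takes up an evaluation. If a trait such as worry about one's own driving raises both uptake and later driving reduction, evaluated DDA drivers and evaluated control drivers are different kinds of people. A comparison between them can then differ with no DDA effect at all. If the evaluation does change driving, adjusting for it would also remove part of the DDA's total effect.

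At stake is the one stated check on this added safety procedure. A distorted result could be read as the evaluation hiding or producing a DDA effect.

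**Working it through.** **The plan's own figure.** The only related number is the Aim 1a sample size of 150 per arm. It reproduces: 50% v 70%, two-sided 0.05, 90% power, continuity-corrected, needs 134 per arm, and 134/0.9 = 149. It does not bear on this point. After 10% loss, 300 × 0.9 = 270 drivers remain (135 per arm), which is used below.

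**Inputs that are assumed.** The documents give no share recommended, no uptake, no driving-reduction rate and no strength of a shared cause. I take control uptake 30%, DDA uptake 30–60%, driving reduction 30% in both arms, and an unmeasured trait U ~ N(0,1) with odds ratio (OR) 1–5 per SD on both uptake E and reduction Y. Neither arm nor evaluation affects Y.

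**Step 1: bias within evaluation status, among recommended drivers.**

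logit P(E=1) = a(arm) + ln(OR)·U; logit P(Y=1) = b + ln(OR)·U

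P(Y=1 | E=e, arm) = ∫ P(Y=1|u) P(E=e|u, arm) φ(u) du / P(E=e | arm)

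| Uptake DDA v control | OR | Evaluated, DDA v control | Not evaluated, DDA v control |
|---|---|---|---|
| 30% v 30% | 3 | 42.7% v 42.7% (0.0) | 24.6% v 24.6% (0.0) |
| 50% v 30% | 1 | 30.0% v 30.0% (0.0) | 30.0% v 30.0% (0.0) |
| 40% v 30% | 2 | 35.1% v 36.1% (−1.0) | 26.6% v 27.4% (−0.8) |
| 50% v 30% | 3 | 38.4% v 42.7% (−4.2) | 21.6% v 24.6% (−3.0) |
| 60% v 30% | 5 | 40.3% v 50.8% (−10.5) | 14.5% v 21.1% (−6.6) |

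Differences are in points, from unrounded values. In the fourth row the arms are equal overall: control 0.3 × 42.7 + 0.7 × 24.6 = 30.0; DDA 0.5 × 38.4 + 0.5 × 21.6 = 30.0. Both strata nevertheless show a deficit in the DDA arm. Both ingredients are needed: with equal uptake or OR 1 the bias is exactly zero.

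**Step 2: whole-trial models.** 2,000 simulated null trials of 270 drivers, with 30% recommended (the plan's share with cognitive impairment, used as a high value):

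| Model | 50% v 30%, OR 3 | 60% v 30%, OR 5 |
|---|---|---|
| Intention to treat | OR 1.00, type I 4.6% | OR 1.00, 5.4% |
| Adjusted for recommendation only | 1.00, 4.6% | 1.00, 5.4% |
| Adjusted for recommendation and evaluation | 0.95, 5.7% | 0.89, 7.4% |
| Recommended drivers, adjusted for evaluation | 0.83, 6.3% | 0.64, 10.3% |

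The simulation error of a 5% rate is √(0.05 × 0.95/2000) = 0.5 points, so 5.7% is within noise. With 10% recommended, the whole-trial OR is 0.99 and 0.96 with no clear inflation.

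**Step 3: dropping evaluated drivers.** Let s be the share flagged, u the reduction rate in unflagged drivers, p the uptake and r the rate in flagged drivers not evaluated. The remaining rate is [(1−s)u + s(1−p)r] / (1−sp). Take s = 0.30 and the fourth row of Step 1.

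- u = 30%: DDA (0.21 + 0.15 × 0.216)/0.85 = 28.5%; control (0.21 + 0.21 × 0.246)/0.91 = 28.8%; difference −0.2.
- u = 10%: DDA (0.07 + 0.0324)/0.85 = 12.0%; control (0.07 + 0.0517)/0.91 = 13.4%; difference −1.3.

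The result depends on how much more often flagged drivers reduce driving, which the documents do not give.

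**Step 4: precision.** If 15% are flagged, 300 × 0.15 = 45, or 22.5 per arm. Uptake of 30% and 50% gives about 7 and 11 evaluated drivers. The standard error at a 30% rate is √[0.21 × (1/6.75 + 1/11.25)] = 22 points. For the whole trial, √(0.21 × 2/135) = 5.6 points.

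**The case against.** The strongest reply is that the analysis being criticised is not written down. The protocol says only that the team will look at whether the recommendation or evaluation affects efficacy. Splitting, excluding or adjusting is an inference about how that would be done. This stands. The point is therefore a safeguard for one branch of an unspecified analysis, not an error in a stated model.

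Second, the recommendation branch may already be a baseline flag. The lower limit of 21 in the rule is the eligibility floor, which suggests that the rule was written for the screening score. A reader might infer that each repeat MoCA prompts new recommendations. The documents do not support that: the repeat is there "a 5-minute MoCA will be repeated to determine current cognitive impairment" and is not tied to the rule. The staff-concern route is firmer ground, because it has no time limit and staff who deliver the intervention know the arm. The branch is thus probably safe as intended, but not as written.

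Third, a reader might infer that the trial's efficacy result is at risk, or that a false arm difference in driving is to be expected. Neither follows. The DCS primary outcome normally precedes any evaluation, the main analyses are by intention to treat, Aim 1c is labelled exploratory, and the sensitivity analysis names no outcome. Every magnitude above is assumed, and 7 v 11 drivers could hardly support a firm conclusion. Imprecision does not remove the bias, but it limits the harm.

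**Conclusion.** The point holds in a limited form. Conditioning the arm effect on an evaluation obtained after randomisation can bias the comparison for follow-up outcomes (Aims 1b and 1c). This requires that the DDA changes uptake and that uptake and outcome share a cause. Both are plausible from the protocol's own description, and neither is documented. The recommendation branch is unbiased if fixed before randomisation; the plan should say that it is.

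The size cannot be derived from the documents. Under the assumptions above it runs from zero to 10.5 points among evaluated drivers, too few for a precise estimate. It is probably small for the whole trial: OR 0.89 to 0.99 when adjusting for evaluation under unequal uptake, and −0.2 to −1.3 points in the worked exclusion example. The primary outcome and the main analyses are unaffected. This is a cheap improvement to a secondary analysis.

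**What to change.** State in the plan that:

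1. The analysis flag uses screening and enrolment values only (MoCA 21–25 and at least 3 risk factors), whatever is later recommended or obtained.
2. The sensitivity analysis is arm by baseline flag, for named follow-up outcomes, with every randomised driver kept.
3. Recommendations made (by route and timing) and evaluations obtained are reported by arm, with the number whose evaluation status is unknown, since drivers may decline to share data.
4. The arm effect is not split, restricted or adjusted by evaluation obtained, or by a recommendation first made after randomisation. If such a table is shown, it is labelled non-randomised and descriptive.

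The cost is wording only. The screening MoCA is already collected, and the risk factors are already reviewed for drivers who score 21–25. No clinical procedure changes. There are two downsides. The analysis no longer isolates drivers who had the evaluation. The flag contrast also cannot separate the recommendation from the impairment that prompts it, so it should be read as effect modification by baseline risk.

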## **Data Safety Monitoring Plan:**

The Principal Investigator ([name]) will be responsible for the ongoing oversight, review, and reporting of adverse events related to the study. [name] will personally review each potential adverse event to determine the course of action, including reporting to appropriate groups, offices, or agencies, or identifying a need for making protocol changes.

A Data Safety and Monitoring Board (DSMB) will also be created to meet NIH requirements for monitoring of clinical trials. Members of the DSMB will be selected based on their expertise in biostatistics, gerontology, and clinical trials. They will be selected from institutions and research groups to minimize conflict of interests with the study's investigators.

In the event that a conflict of interest within the IDMC is identified, it will be disclosed to COMIRB. The DSMB will also provide recommendations to the PI on how to resolve the conflict of interest, which will then be reported to NIA and COMIRB. If a resolution cannot be found, a new member will be appointed to the DSMB.

The first task of the DSMB will be to approve the DSMB charter, which outlines procedures including meeting frequency. The DSMB will meet twice yearly or as-needed, such as in the event of a SAE. Any DSMB recommendations to amend the protocol will be reviewed and approved by Colorado Multiple Institutional Review Board (COMIRB) before implementation of proposed changes. The DSMB will review and evaluate study progress, data quality, risks and benefits, and other factors that will influence the overall study outcomes, safety, and feasibility during biannual meetings. Data reviewed by the DSMB will identify participants by their study ID only. If confidentiality is lost, the appropriate actions will be taken based on institutional policies. The DMSB will review data and make recommendations on any concerns or adverse events related to the study. These recommendations include altering or stopping with respect to safety concern for participants. Although not expected in this study, any serious adverse events will be reported to COMIRB, the DSMB, and NIA within 48 hours.

The DSMB will deliver an annual report to NIA, unless a report is requested more frequently. This report will include information on the safety and progress of the study. This report will include a summary of any AEs or SAEs and provide recommendations about whether the study should be continued, modified, or terminated.

Adverse Events and Serious Adverse Events: Adverse and serious adverse events will be defined based on guidance from Colorado Multiple Institutional Review Board and the NIH. An Adverse Event (AE) is any unfavorable and unintended sign (including abnormal laboratory finding), symptom, or disease temporally associated with the use of a medical treatment or procedure, regardless of whether it is considered related to the medical treatment or procedure (attribution of unrelated, unlikely, possible, probable or definite). A serious adverse event (SAE) includes any untoward medical occurrence that at any dose results in death or the immediate risk of death, hospitalization or prolonging of an existing hospitalization, persistent or significant disability/incapacity or a congenital anomaly/birth defect (NIH guide-6/11/99).

The DSMB will review any unexpected events that may occur with study participants to determine whether the event is considered an adverse event, and if the event is study related. Research staff will alert the Site PI and [name] to any potential AE or SAE, who will assist with arranging any needed services for the participant. Within 48 hours of discovery of a SAE, it will be reported to COMIRB, and within one week to the DSMB and study's assigned project officer. Within two weeks of an AE being discovered, it will be reported to COMIRB, the project officer, and DSMB. In all cases, the PI, under advice of COMIRB, will determine what further, assessment, follow-up or action is required for an AE or SAE. A summary of SAEs that occurred during the study year will be part of the annual progress report that is submitted to both COMIRB and NIA. If it is unclear if an event meets criteria for a SAE by definition, the PI will refer it to the DSMB to determine if it meets SAE definition.

#### **Description, Risks and Justification of Procedures**

#### **Risks to Human Subjects:**

This is a minimal risk study. One risk of this study is loss of privacy due to breach of confidentiality. We will make every attempt to keep information private. Screening logs will not contain any identifying information. To ensure adequate protection of confidentiality, any age above 89 will be treated as an identifier and will be recorded as 89+ in screening logs. Data will be stored in a secure, password protected database on the University of Colorado server, (or equivalent institutional servers at other sites), with access limited to study personnel. Some participants may be uncomfortable discussing driving. They may choose not to answer certain questions. The research team will report any activities resulting in participant discomfort or injury to the IRB immediately.

Older adult drivers will be asked questions related to their driving behavior in addition to measures related to physical health, cognitive impairment, and decision-making capability. Mandatory reporting of potential driver impairment due to medical conditions varies by state. Of note, in this study we will not be assessing actual driving function, and no single question or cognitive test is accurate in identifying driving risk. Driving cessation itself comes with risks, so the study team will not automatically report drivers with particular MoCA scores. However, during the informed consent process, we will explain the study protocol related to participants who have clear visual, cognitive or functional deficits suggesting a driving safety concern, and individuals must agree to the protocol in order to enroll. In identifying potential impairment, research staff will draw upon evidence and impressions from responses as well as participant observation; examples might include a participant who is unable to remember the question just asked, who is disoriented to the purpose of the questions, who mentions a diagnosis of cognitive impairment/dementia or new difficulties with memory, who mentions new significant

AUTO Study Protocol: Version Date: 12/22/21

PI: [name], MPH COMIRB No: 19-0059

physical limitations (including site, reflexes and strength), or who mentions problems with driving. In such cases, the research staff member would document the date and specific observations and review the issue with the Site PI. If the concerns are deemed relatively mild, the study team will provide the participant with information on community resources for driving assessment and rehabilitation and will recommend that they discuss their driving with their primary care provider. If the concerns are deemed more serious than "relatively mild," the study team would similarly provide information (including specific concerns) to the participant with the written recommendations that they talk with their primary care provider and/or have a driving safety evaluation and that they not drive until cleared. The informed consent form gives participants the option of allowing the research team to contact a primary care provider and/or another designee if the investigators' concerns about driving risks are more serious than "relatively mild." If consent was given, the study team would reach out to the designated person or people to express their concerns about the subjects' driving safety. Otherwise, additional survey responses will not be shared with anyone who is not involved with the study (including physicians, family members, or hospital or law enforcement authorities) unless specifically requested by the participant, this includes the co-enrolled family member or friend.

This study will enroll older adults who potentially may experience mild to moderate levels of cognitive impairment, creating a potential risk for informed consent for study participation. Level of impairment will be measured through administration of the 5-minute MoCA during an initial phone screen; the participant must score ≥21 to be eligible to be scheduled for an enrollment visit. While completing the consent process during the initial study interview (in person or remotely, via phone), staff will ask a series of questions to determine understanding of study procedures. In the event there is cognitive concern, the participant will not be allowed to enroll in the study.

At each follow up for all drivers and study partners, a 5-minute MoCA will be repeated to determine current cognitive impairment. As all participants have completed informed consent at initial enrollment, potential diminished cognitive capacity does not limit the participant's right to continued participation in follow up calls. During consent at enrollment, participants will have reviewed study requirements, tasks, duration, and an explanation that all participants have the right to continue or withdraw as they wish. Therefore, cognitive impairment will not automatically withdraw a participant from the study. Further, this study poses minimal risk to the participant. In the event that severe cognitive impairment disrupts the research team's ability to collect follow up data from the participant, the study team may choose to discontinue all or specific portions of follow-up procedures.

Because of the study's affiliation with clinical sites, there is the potential risk of coercion. We will minimize this risk by being very clear that participation is completely voluntary, separate from their clinical care, and that a participant can withdraw from the study at any time. Additionally, we will make clear that the patient's clinical care will not be impacted by the decision to participate or not to participate. No clinicians or providers from the participating clinics will be involved in the consenting of patients. There will be no exchange of payment for study participant referrals.

This study will not involve pregnant women, human fetuses, neonates, children, or prisoners. Study participation will not interfere with clinical care. The study informed consent form will include a written description of all of these risks, including the potential for eventual driving AUTO Study Protocol: Version Date: 12/22/21 PI: [name], MPH COMIRB No: 19-0059 cessation due to study participation, and all of these risks will be discussed during the informed consent process. This study will not enroll older adults with severe cognitive impairment.

